## 2.3 Data collection

### Methods

As the present study's results will be compared with the results of the HPSF quasi-experimental trial (NCT02800616), the majority of the outcome measures and data collection methods used in the present study will be equal to the outcome measures and data collection methods used in the HPSF trial. The main difference with the original HPSF trial is the fact that the amount of measurements within this project will be smaller than in the original trial.

### Study Procedures

As shown in Table 1, outcome measurements will be gathered via various sources. Via the school system, data will be gathered regarding background variables and school absenteeism, which was also done in the HPSF trial. At Prisma, one contact person is assigned for HCCF. This person is also responsible for data supply for this study. With regard to the data collected from the school system, a data transfer agreement between educational board Prisma and Maastricht University has been composed and will be signed after ethical approval of the study has been obtained.

The majority of the additional data will be gathered during a 'research week' in the class. All measurements in children will be administered during class hours. At the beginning of this week, participants will receive two questionnaires that are similar to those used in the HPSF trial. The estimated time to complete these questionnaires is 40 minutes. The questionnaires contain questions regarding children's PA and dietary behaviours and children's well-being. Unlike in the HPSF trial, where the questionnaires were filled out in writing, the questionnaires will be completed digitally in the current study. This is done as all children have access to a tablet with a working WIFI-connection. Filling out the questionnaires digitally will limit time and effort for both participants and researchers. Most children will fill out the questionnaires independently. However, the children in study year four will fill out the questionnaires together with a researcher in the class. Next to these two questionnaires, children will fill out a short questionnaire regarding their psychosocial determinants of fruit and vegetable intake. This questionnaire will be administered in writing during the first research week, three weeks after the first research week and three months after the first research week. Measurements of bodyweight, height and waist/hip circumference will be done during the research week, using the same protocol that was used in the HPSF trial and by integrating measurements in the school hours that are allocated to PA education. A team of researchers will supervise administration of all measurements. The researchers will be trained according to a strict protocol (equal to the HPSF protocol) to prevent interrater differences. Additionally, trained research assistants will observe the schoolyard during lunch breaks to investigate any differences in children's free play. Parents/caregivers will also receive a digital questionnaire (similar to the questionnaire used in the HPSF trial) during the research week. The digital questionnaire contains questions regarding children's PA and dietary behaviours and children's health and well-being. Parents/caregivers are asked to complete the questionnaire within ten days. They can return the questionnaire online, or if preferred, by means of a letterbox in the school or regular postal mail.

Teachers will receive a short online questionnaire regarding their students' behaviour in class (e.g., concentration during lessons, class atmosphere), their activities regarding health in class and their appreciation of the project. Pedagogical employees will also receive a short online questionnaire assessing their appreciation of the project. Lastly, childcare centre directors will receive a questionnaire in which they are asked to describe the childcare centre's health-related policies.

#### **Data collection**

The principal investigator, together with research assistants and students, will collect all data for this study.

#### **Standardising**

The researchers will be trained according to a strict protocol to prevent interrater differences. This protocol is equal to the protocol used in the original HPSF trial and is therefore already available for use.

## **2.4 Data analyses**

#### **Data inspection**

Extreme and missing values will be identified and handled in IBM SPSS Statistics for Windows (version 25, IBM Corp, Armonk, NY, USA). This will be done using the same syntaxes that were used in the HPSF trial. Using these syntaxes, missing values will automatically be coded, while differentiating between system missing values and user missing values. The cut-off scores for extreme values of questionnaires and anthropometric measurements used in the HPSF trial will again be used in the current study. Additionally, longitudinal cleaning checks will be executed.

#### **Normal distribution**

Normal distribution of the data will be tested in IBM SPSS Statistics for Windows (version 25, IBM Corp, Armonk, NY, USA) using histograms and Q-Q plots.

#### **Descriptive statistics**

Using IBM SPSS Statistics for Windows (version 25, IBM Corp, Armonk, NY, USA), descriptive statistics will be used to describe participants' background characteristics.

#### **(Interim)analyses**

Linear mixed model analysis techniques will be used to assess the longitudinal effect of HCCF on numerical outcome variables, as this technique corrects for correlation within individuals within groups, which occurs in repeated-measures research designs. Another advantage of this technique is that it naturally handles missing values, in case data are missing at random. Since measurements are repeated within participants, who are nested within childcare centres, we use a three-level model with childcare centres as third level, participants as second level and measurements as first level. The fixed part of the model consists of group (distribution based on Diffusion of Innovations Theory), time (time-points at which the measurements are taken) and the interaction term group\*time. Baseline variables that are related to missing data and/or outcome will also be included to obtain unbiased results and/or to gain precision. As for the random part of the model, a random intercept on childcare centre level will be included next to an unstructured covariance structure for the repeated measurements.

For categorical outcome variables, a logistic mixed model analysis technique will be used, where the model is similar as described for the numerical outcome variables.

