**Main parameters/endpoints:** The main study parameter of the effect evaluation is the change in absolute BMI z-score, which will be compared between the childcare centres that are categorised based on their degree of implementation (using categories based on the Diffusion of Innovations Theory).

**Methods:** Data will be collected in the form of questionnaires (parents, children, teachers/pedagogical employees, directors), anthropometric measurements (children), interviews (teachers/pedagogical employees, directors), observations and analyses of minutes of meetings.

**Nature and extend of the burden and risks associated with participation:** No intervention is allocated in this study other than activities planned by childcare centres in accordance with wishes and needs of childcare centre staff and parents. All outcome measures are non-invasive. The measurement protocol was designed while taking into account both a minimal burden for participants and a relevant scientific output for stakeholders (e.g., school board, teachers, parents/caregivers and children). Burden of participants is minimised by incorporating most measurements in the regular school day.

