### Effect evaluation:

- *Primary outcome:* At two-year follow-up, is there a difference in absolute BMI z-score between children from different childcare centres, which have been categorised based on their level of innovativeness and implementation?
- *Secondary outcomes:*
  - ➔ At two-year follow-up, is there a difference in waist/hip circumference between children from different childcare centres, which have been categorised based on their level of innovativeness and implementation?
  - ➔ At two-year follow-up, is there a difference in physical activity behaviours of children from different childcare centres, which have been categorised based on their level of innovativeness and implementation?

- ➔ At two-year follow-up, is there a difference in dietary behaviours of children from different childcare centres, which have been categorised based on their level of innovativeness and implementation?
  - ➔ At two-year follow-up, is there a difference in health markers of children from different childcare centres, which have been categorised based on their level of innovativeness and implementation?
- At two-year follow-up, is there a difference in school well-being of children from different childcare centres, which have been categorised based on their level of innovativeness and implementation?

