## 2.2 Recruitment and selection of participants

### Study population

A closed design will be used, meaning that at baseline (T0), all children in study year four to six of the Prisma childcare centres will be invited to participate in the study. At T1, these children will be students in study year five to seven, and at T2 they will be in study year six to eight. Based on the amount of children enrolled in school year 2019/2020, approximately 685 children are eligible to participate in the study.

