### Number of anticipated participants

Childcare centres are free to choose if, when and to what degree they implement HCCF changes in their childcare centre. After data collection, the twelve childcare centres will be divided into three categories based on the Diffusion of Innovations theory (innovators/early adopters, early/late majority, laggards) (35). Because this categorisation occurs after data collection, it cannot yet be predicted which childcare centres will fall under which category. However, based on the childcare centres' intentions that have become clear during preliminary discussions about the project, three potential scenarios can be illustrated where childcare centres are categorised within the three groups. These scenarios are further illustrated in the light of three sample size calculations that allow for clustered sampling. For the calculations, the following website is used: <http://www.sample-size.net/means-effect-sizeclustered/> (36).

The sample size calculation was based on the primary outcome, i.e. to detect a difference in mean absolute BMI z-score between innovators/early adopters and laggards after two years intervention. The following general assumptions were used for the sample size calculation:

- Independent-samples t-test on difference in absolute BMI z-scores;
- Children are nested within schools;
- A significance level (alpha) of 0.05;
- A power of 80%;
- A dropout rate of 10%, as based on dropout rates observed by Bartelink et al.(33);
- An Intraclass Correlation Coefficient of 0.01, as based on Amorim et al. (37);
- Unequal cluster sizes with a relative efficiency of 90% (38);
- An average absolute BMI-z of 0.76 and an SD of 0.60 in the population (as no data was available for the population in Peel en Maas, these values were calculated over all children aged between 4 and 11 living in region Parkstad who visited the Youth Health Department in 2013).

### Scenario 1

- *Innovators/early adopters*: three childcare centres, number of participants (N1)=120
- *Laggards*: four childcare centres, number of participants (N3)=220
- Average size of each cluster (m): 50

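### If change from T0 to T2 is the primary contrast, the planned centre intercept cancels and the standard error ignores clustering of change within centres; the plan does not say which contrast is primary

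*Combined protocol and SAP*

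**What the plan says.** The Summary (Main parameters/endpoints) states: "The main study parameter of the effect evaluation is the change in absolute BMI z-score". Section 1.1 words the primary question as a comparison at one time: "At two-year follow-up, is there a difference in absolute BMI z-score between children from different childcare centres". The sample size in section 2.2 (Number of anticipated participants) is set "to detect a difference in mean absolute BMI z-score between innovators/early adopters and laggards after two years intervention", and assumes "An Intraclass Correlation Coefficient of 0.01" without saying that this refers to change.

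Section 2.4, under (Interim)analyses, says: "Linear mixed model analysis techniques will be used to assess the longitudinal effect of HCCF on numerical outcome variables". The fixed part is group, time and group*time. For the random part, "a random intercept on childcare centre level will be included next to an unstructured covariance structure for the repeated measurements". There is no centre-by-time term and no primary contrast is named. The section adds: "Baseline variables that are related to missing data and/or outcome will also be included to obtain unbiased results and/or to gain precision". It does not say whether baseline BMI z is one of these covariates or the first of three outcomes.

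**The concern.** Group is assigned to whole centres, 12 in all and 7 to 9 in the comparison of innovators/early adopters with laggards. Each centre chooses its own measures, so centres within a category may well differ in how BMI z develops. A valid standard error for a group difference in change has to reflect that.

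A centre intercept that is constant over time describes differences in level only. It drops out of a within-child change, so the three-level model would look as if it handled clustering while giving the change contrast no protection. The confidence interval would be too narrow, and chance differences between centres could be read as implementation effects and carried into the planned link with the process evaluation.

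**Working it through.** The documents state no type I error beyond the nominal 0.05, so there is no figure to reproduce except 5% when centres do not differ in change. Two-sided testing is assumed, since sidedness is not stated. The detectable effect sizes in section 2.2 are not used.

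**1. Cancellation.** Write the centre effect as u, the same at every visit. In T2-T0 it contributes u - u = 0. As a numerical check, take SD 0.60 (section 2.2), an assumed child T0-T2 correlation of 0.8, and 12 centres of 49 children, four per group. The child variance of change is 2 × 0.36 × (1 - 0.8) = 0.144. The planned standard error of the contrast is √(2 × 0.144/(4 × 49)) = 0.0383, and it stays at 0.0383 for a centre-intercept variance of 0, 0.0036 or 0.02. The standard error of the T2 level contrast rises from 0.061 to 0.074 and 0.117 over the same values. So the intercept protects the level contrast but not the change contrast. A second calculation with unequal centres, complete or with 10% missing at T2, showed the same.

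**2. What is left out.** Between-centre variance in change is absorbed into the child-level unstructured covariance. What the standard error omits is the correlation of changes within a centre. The variance is therefore too small by the factor 1 + (m - 1) × ICC, with m children per centre and the ICC of change. At ICC 0.01 and m = 49 the factor is 1.48, and the true standard error is about 0.0469.

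**3. Children per centre.** The three scenarios give 340/7, 434/8 and 520/9. After 10% dropout these are 43.7, 48.8 and 52.0. As "approximately 685 children are eligible to participate in the study", or 685/12 = 57.1 per centre, the scenarios need 85-101% participation. With 50-60% participation (assumption) and 10% dropout, m is 25.7 to 30.8.

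**4. Type I error** = 2 × (1 - Φ(1.96/√(1 + (m - 1) × ICC))). For m = 48.8 and ICC 0.01: √1.478 = 1.216, 1.96/1.216 = 1.61, giving 10.7%.

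| Assumed ICC of change | m = 43.7-52.0 | m = 25.7-30.8 |
|---|---|---|
| 0 | 5.0% | 5.0% |
| 0.005 | 7.5-8.0% | 6.4-6.8% |
| 0.01 | 10.1-11.1% | 7.9-8.5% |
| 0.02 | 15.0-16.8% | 10.9-12.1% |

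Simulation of the change test at ICC 0.01 with the scenario sizes gave 10.1-11.9%, and 13.1% with strongly unequal centres, so 11% is not an upper limit.

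**5. From a level ICC to a change ICC.** Suppose the 0.01 in section 2.2 is for level. Let r be the child T0-T2 correlation and c the correlation of centre effects between T0 and T2. The ICC of change is 0.01(1 - c)/(0.01(1 - c) + 0.99(1 - r)). Type I error at m = 49:

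| c | r = 0.7 | r = 0.8 | r = 0.9 |
|---|---|---|---|
| 0.9 | 6.9% | 7.9% | 10.7% |
| 0.99 | 5.2% | 5.3% | 5.6% |

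Both correlations are assumptions.

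**6. Other readings, at change-ICC 0.01.** With baseline BMI z as a covariate and T1 and T2 as outcomes (simulated, 49 per centre), type I error is 6.4-8.7% with a normal test and 4.8-6.9% with Satterthwaite degrees of freedom. The lower ends apply if centre deviations are constant from T1, the upper ends if they grow linearly. For the T2 level difference it is 5.8-6.6% by formula and 4.5-4.8% with Satterthwaite degrees of freedom.

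**The case against.** The strongest reply is that the problem exists on one reading of the plan. The two places that tie a primary outcome to a comparison, section 1.1 and the sample size in section 2.2, both describe the difference after two years. Only the Summary says change, and a group*time model can deliver either contrast. On the level reading the omission matters little, and with baseline as a covariate it is reduced. This stands, and it is why the point is conditional. It does not remove the point, because the Summary names change as the main parameter and section 2.4 speaks of a longitudinal effect without choosing.

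A second reply is that the size rests on figures the documents do not give: the ICC of change, the correlations over time and the participation rate. That also stands. With nearly stable centre effects the error stays close to 5%.

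Three stronger readings are tempting. A reader might infer that the planned analysis has an 11% error rate; that needs change as the primary contrast, an ICC of change of 0.01 and near-full participation, and the documents establish none of these. A reader might infer that the model ignores clustering altogether; it does not, since the intercept protects the level contrast. Or one might say that all between-centre variation in change is left out; that variation does enter the child-level variance, and only the within-centre correlation is missing.

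**Conclusion.** The concern holds conditionally. If T2-T0 is the primary contrast and T0, T1 and T2 are all outcomes, the planned standard error does not account for clustering of change. That mechanism is exact with complete data, and confidence in it is high. Confidence in its size is moderate: the inflation runs from none, if centres do not differ in change, to roughly a doubling of the nominal 5% at an assumed ICC of change of 0.01 with 44-52 children per centre. What needs no assumption is that the Summary and sections 1.1, 2.2 and 2.4 do not settle which contrast is primary, and that this choice decides whether the model handles clustering. Because the effect evaluation is a secondary objective of an observational study, this should be fixed but is not critical.

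**What to change.** 1. In section 2.4, add a random centre slope for time to the linear mixed model and test group*time with Satterthwaite degrees of freedom. In simulations with complete data, equal centre sizes, four centres per group and 49 children per centre, this gave 4.5-4.9% at change-ICC 0.01. A single equal-variance centre-by-visit component is not enough: it gave 6.8-7.8% when centre deviations persisted or grew.
2. Report as a sensitivity analysis a comparison of the 12 centre mean changes by group (12 - 3 = 9 residual degrees of freedom), weighted or otherwise allowing for unequal centre sizes. It is needed because the slope variance is estimated as zero in about a quarter of trials at change-ICC 0.01 with 49 per centre. The model then returns the planned, too-narrow interval, and type I error among those trials is still about 11%. The allowance for size matters: with unequal centres an unweighted version rejected in about 5.8% (change-ICC 0.01) to 7.5% (change-ICC 0, strongly unequal sizes).
3. Name the primary contrast, T2-T0 or the T2 difference, and say whether baseline BMI z is an outcome or a covariate, so that the Summary and sections 1.1, 2.2 and 2.4 agree.

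The cost is one model term, one clarifying statement and one sensitivity analysis, with no new data. At change-ICC 0.01, 49 per centre and an assumed T0-T2 correlation of 0.8, the 95% half-width rises from 1.96 × 0.0383 = 0.075 to about 0.100-0.106 BMI z (upper end: 2.262 × 0.0469, with 9 degrees of freedom). If centres do not differ in change, the test is somewhat conservative, at about 3.5%.

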#### **Coding and interpretation**

All qualitative data will be recorded, transcribed and coded using Nvivo software. Coding will be performed by two independent researchers. Peer consultation between researchers will frequently take place. Major themes and discrepancies will be discussed with a third senior researcher. All researchers involved in data collection and analyses will keep a self-reflective diary to evaluate their own subjective views on the interpretation of the data.

#### **Software programme**

Quantitative data will be analysed using IBM SPSS Statistics for Windows (version 25, IBM Corp, Armonk, NY, USA). Qualitative data will be analysed using Nvivo software.

## 2.5 Data management

### Location

To assure correct and safe data management and to ensure that the highest standards of academic integrity are maintained, a data management plan according to the FAIR principles (Findable, Accessible, Interoperable, and Reusable) will be developed for this study. This plan outlines the plans for storage, sharing and preservation of the data during and after the study. Additionally, it describes the security measures that will be taken and the restrictions that will apply given the nature of the data.

All data will be stored according to the Maastricht University Data Management Guidelines (Table 2).

**Table 2: Storage Locations and Back-Up**

|  | Non-digital data
(e.g., paper) | Digital data   | Back-up  |
|--|---|---|---|
| Non-sensitive data                    | No restrictions                           | No restrictions   | Network discs   |
| Sensitive, pseudonymised data         | Locked closet in a locked room            | Only on network discs. When the file size is too large to store on network discs, an alternative and safe storage location will be chosen after consultation of the principal investigator. | Network discs   |
| Sensitive, pseudonymised data with ID | Locked closet in a locked room            | Only on network discs. When the file size is too large to store on network discs, an alternative and safe storage location will be chosen after consultation of the principal investigator. | Network discs   |
| Sensitive data with personal data     | Locked closet in a locked room            | Only on a separate network disc. Only the principal investigator and the coordinating investigator have access to this data.  | Only on a separate network disc. Only the principal investigator and the coordinating investigator have access to these back-ups. |

### Data access

All researchers involved in data collection procedures during the project will have access to research data. The principal investigator, the coordinating investigator and the research assistants will have access to the complete data set (i.e., sensitive data with personal data). The project leader will have access to the pseudonymised data set.

